8.1 Definitions

Unanticipated Problems Involving Risk to Subjects or Others (UPIRTSO)

Any unanticipated problem or adverse event that meets the following three criteria:

- •Serious: Serious problems or events that result in significant harm, (which may be physical, psychological, financial, social, economic, or legal) or increased risk for the subject or others (including individuals who are not research subjects). These include: (1) death; (2) life threatening adverse experience; (3) hospitalization- inpatient, new, or prolonged; (4) disability/incapacity-persistent or significant; (5) birth defect/anomaly; (6) breach of confidentiality and (7) other problems, events, or new information (i.e. publications, DSMB reports, interim findings, product labeling change) that in the opinion of the Principal Investigator and/or Investigators may adversely affect the rights, safety, or welfare of the subjects or others, or substantially compromise the research data, AND
- •Unanticipated: (i.e. unexpected) problems or events are those that are not already described as potential risks in the protocol, consent document, not listed in the Research Participant Consent and Privacy Authorization Form, or not part of an underlying disease. A problem or event is "unanticipated" when it was unforeseeable at the time of its occurrence. A problem or event is "unanticipated" when it occurs at an increased frequency or at an increased severity than expected, **AND**

•Related: A problem or event is "related" if it is possibly related to the research procedures.

Adverse Event

An untoward or undesirable experience associated with the use of the study formulation in a research subject.

Serious Adverse Event

Adverse events are classified as serious or non-serious. Serious problems/events are defined as events that:

- result in death
- are immediately life threatening
- result in a new or prolong and existing hospitalization
- result in disability/incapacity; or
- are persistent or significant birth defect/anomaly

And/or per protocol may be problems/events that in the opinion of the Principal Investigator and/or Investigators may have adversely affected the rights, safety, or welfare of the subjects or others, or substantially compromise the research data.

All adverse events that do not meet any of the criteria for serious, should be regarded as non-serious events.

Adverse Event Reporting Period

For this study, the study treatment follow-up period is defined as the last scheduled visit.

Preexisting condition

A preexisting condition is one that is present at the start of the study. A preexisting condition should be recorded as an adverse event if the frequency, intensity, or the character of the condition worsens during the study period.

General Physical Examination Findings

At screening, any clinically significant abnormality should be recorded as a preexisting condition. At the end of the study, any new clinically significant findings/abnormalities that meet the definition of an adverse event must also be recorded and documented as an adverse event.

Post-study Adverse Event

All unresolved adverse events are to be followed by the Principal Investigator and/or Investigators until the events are resolved, the subject is lost to follow-up, or the adverse event is otherwise explained. At the last scheduled visit, the Principal Investigator and/or Investigators should instruct each subject to report and any subsequent event(s) that the Participant, or the Participant's personal physician, believes might reasonably be related to participation in this study.

Abnormal Laboratory Values

A clinical laboratory abnormality that can reasonably be related to the administration of the study formulation should be documented as an adverse event.

Page 17 of 32

Hospitalization, Prolonged Hospitalization or Surgery

Hospitalization, prolonged hospitalization, or surgery is to be reported as an adverse event if it can reasonably be related to the administration of the study formulation.

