4.4 Early Withdrawal of Subjects

4.4.1 When and How to Withdraw Subjects

Patients are free to withdraw at any time and for whatever reason. No data will be collected for withdrawn subjects and withdrawn subjects will not be replaced. There will be no follow-up for withdrawn subjects. Pre-specified reasons for discontinuing include, but are not limited to, the following:

- Patient request: Patient decided that he/she did not want to continue (for any reason).
- •Adverse Event: Patient experienced a related or unrelated event that would interfere with the study objectives/evaluation
- •Lost to Follow-up: Patient did not come in for a visit and could not be reached by phone
- Treatment Failure: If in the Principal Investigator's judgment, the patient's condition required another form of treatment
- •Noncompliance: Patient is not complying with the protocol requirements (i.e. visit schedule, dosing, regimen, etc.); a patient is to be withdrawn if he/she misses two consecutive visits
- •Other: Any other reason

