8.2 Recording of Adverse Events

At each contact with the subject, the Principal Investigator and/or Investigators must seek information on adverse events by specific questioning and, as appropriate, by examination. Information on all adverse events should be recorded immediately in the appropriate adverse event section of the Case Report Form. All clearly related signs and symptoms should be recorded.

All adverse events occurring during the study period must be recorded. The clinical course of each event should be followed until resolution, stabilization, or until it has been ultimately determined that the study treatment or participation is not the probable cause. Serious adverse events that are still ongoing at the end of the study period must be followed up, to determine the final outcome. Any serious adverse event that occurs after the study period and is considered to be at least possibly related to the study treatment or study participation will be recorded and reported immediately.

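### Section 8.1 counts hospitalization, surgery and laboratory abnormalities as adverse events only if judged related, which conflicts with 4.4.1, 8.2 and 8.3.1 and can under-count unsolicited events

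*Combined protocol and SAP*

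**What the plan says.** Section 8.1 (Definitions) defines an adverse event as "An untoward or undesirable experience associated with the use of the study formulation in a research subject". It does not add that an event counts whether or not it is thought to be caused by the formulation.

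Specific rules follow in the same section:

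- For surgery and for new or longer hospital stays, the rule is that such an event "is to be reported as an adverse event if it can reasonably be related to the administration of the study formulation".
- For laboratory results: "A clinical laboratory abnormality that can reasonably be related to the administration of the study formulation should be documented as an adverse event".
- For existing conditions there is no relatedness test: "A preexisting condition should be recorded as an adverse event if the frequency, intensity, or the character of the condition worsens during the study period".
- New findings at the end of the study are recorded if they satisfy the general definition.

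The serious-event list in 8.1 includes a new or prolonged hospitalization, and that item carries no relatedness condition.

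Section 8.2 (Recording of Adverse Events) says: "All adverse events occurring during the study period must be recorded". Events are followed to resolution or stabilization, or "until it has been ultimately determined that the study treatment or participation is not the probable cause". It adds "All clearly related signs and symptoms should be recorded", without saying whether that means related to the drug or to the event. Section 8.3.1 lists the relationship to the research among the items documented for each adverse event. In section 4.4.1 the withdrawal reason headed Adverse Event reads "Patient experienced a related or unrelated event".

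**The concern.** Relatedness is best recorded as an attribute of an event after the event has been written down. For hospitalization, surgery and laboratory abnormalities, section 8.1 makes it a condition of entry. The general definition can be read the same way.

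The study has one group of 10 patients and is open label (sections 3.1, 5.5 and 7.1). There is no control group to show a background rate, and the person judging causality knows that every patient is treated. That is inherent in the design. What can be avoided is making the judgment before the event is recorded, because an adverse event listing cannot later recover what was never entered.

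The events most exposed are unsolicited ones. The background (section 1.1) names somnolence, dyskinetic symptoms, impaired performance and anticholinergic symptoms as possible effects of excessive absorption of topical antihistamines. None of these is among the four solicited items in section 3.4, which are itching, swelling, stinging or burning, and dryness. Section 3.4 also expects minimal systemic absorption, which may incline an investigator to call such symptoms unrelated. Section 8.6 bases medical monitoring partly on the number and type of serious adverse events, and the hospitalization rule can lower that count.

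**Working it through.** The plan states no adverse event rate, safety power or numeric stopping threshold, so there is no figure to reproduce. The check is a comparison of passages, followed by an illustration of scale.

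**Step 1: two readings of the general definition.**

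- *Association in time.* Any untoward experience during use is an adverse event, and 8.2 requires all of them to be recorded. The hospitalization, surgery and laboratory rules then conflict with 8.2, because they leave out events that the general definition admits.
- *Association by cause.* Only related experiences are adverse events. Sections 8.1 and 8.2 then agree formally, since 8.2 uses the term that 8.1 defines. The definition now conflicts with the unrelated events in 4.4.1 and with the 8.2 follow-up rule, under which a recorded event can prove not to be caused by treatment. It also fits poorly with the relationship field in 8.3.1, although that field could still grade degrees of relatedness.

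Neither reading makes the sections consistent.

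**Step 2: one event traced through.** Suppose a patient is admitted in week 1 and the investigator thinks the formulation is not involved. The serious-event list covers a new hospitalization. The hospitalization rule in 8.1 does not make it an adverse event. Section 4.4.1 would accept it as an adverse event reason for withdrawal. Two staff members, each following the protocol, could record it differently.

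**Step 3: what is not filtered.** The four solicited skin scores are rated 0 to 3 by investigator and participant at both visits, with no relatedness condition (section 3.4). Worsening of existing conditions has none either. Serum tryptase and the three urinary mediators are measured at week 2 as secondary endpoints, whether or not a value is called an adverse event (sections 3.3 and 6.5).

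**Step 4: scale, for illustration only.** Input from the plan: n = 10. Assumed, because the documents do not give them: the per-patient rate p of an unsolicited event and the fraction f that passes the relatedness screen. Patients are taken as independent, with at most one event each.

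Chance of recording at least one event = 1 − (1 − pf)^10.

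| p | f = 1 (all recorded) | f = 0.5 | f = 0.25 |
|---|---|---|---|
| 10% | 65% | 40% | 22% |
| 20% | 89% | 65% | 40% |
| 30% | 97% | 80% | 54% |

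For example, p = 20% and f = 0.5 gives 1 − 0.9^10 = 65%, against 1 − 0.8^10 = 89% with full recording.

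Leaving out one patient's only event changes 1/10 (exact two-sided 95% interval 0.25% to 44.5%) to 0/10 (0% to 30.8%, where 30.8% = 1 − 0.025^(1/10)).

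**The case against.** The strongest reply is that the protocol as a whole means unrelated events to be recorded. Where 8.1 intends causality it uses a form of the word related, so the looser phrase in the general definition may mean association in time. The follow-up rule, the relationship field, the withdrawal wording and the rule on existing conditions all fit that intent. This stands as far as the general definition goes: that sentence alone does not establish a causal filter. It does not explain away the hospitalization, surgery and laboratory rules, whose condition is explicit.

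A reader might infer more than the text supports in four ways:

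- *That the tolerability result is biased.* The primary safety endpoint is the set of solicited skin scores, analysed as proportions per category (section 7.2.1), and no relatedness test touches it. The plan specifies no analysis of adverse event rates.
- *That filtered events vanish before anyone can see them.* Visit 2 separately reviews changes in medical history and medications (section 6.5), adverse events are sought by specific questioning (section 8.2), and monitors have access to subject records (section 10.1). An event may appear there without being classed as an adverse event.
- *That the 30.8% limit measures the defect.* It describes a sample of 10 with no events and would be the same under any definition. It is also the upper end of a two-sided interval; the one-sided 95% limit is 25.9%.
- *That limiting IRB reports to directly related serious events (section 8.3.1) is part of the filter.* That sentence governs onward reporting, not recording.

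The laboratory rule also has little practical effect, because the scheduled post-baseline tests are kept as endpoints anyway. And the hospitalization rule speaks of reporting the admission; it does not say that the underlying illness goes unrecorded.

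**Conclusion.** The concern holds in a limited form. Section 8.1 puts an explicit relatedness condition on hospitalization, surgery and laboratory abnormalities, and sections 4.4.1, 8.2 and 8.3.1 treat relatedness as something judged about an event already recorded. These passages must be reconciled. The practical risk is under-counting of unsolicited events: chiefly hospitalization and surgery, and also possible systemic antihistamine effects if the general definition is read causally.

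The documents do not allow the loss to be estimated. Under the assumed rates of 10% to 30% and with half of events screened out, the chance of seeing at least one event in 10 patients falls by 17 to 25 percentage points (97% to 80% at a 30% rate, 65% to 40% at a 10% rate). This rests on the assumed screening fraction and on investigators applying the rule literally. It matters mainly because section 7.1 says the pilot is to inform a larger study, and a low count of unsolicited events is informative only if recording was complete.

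**What to change.** In section 8.1:

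- Define an adverse event as any untoward occurrence in a participant after the first application of the formulation, whether or not it is considered related.
- Delete the relatedness condition from the rules on hospitalization, prolonged hospitalization, surgery and laboratory abnormalities.
- Leave the rule on worsening of existing conditions as it is.

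Capture causality in the relationship field that 8.3.1 already provides. In 8.2, state what the signs and symptoms must be related to.

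The cost is a change of wording and a few more entries for 10 patients over two weeks. Treatment, visits, endpoints and the rules for onward reporting stay as they are.

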8.2 Recording of Adverse Events

At each contact with the subject, the Principal Investigator and/or Investigators must seek information on adverse events by specific questioning and, as appropriate, by examination. Information on all adverse events should be recorded immediately in the appropriate adverse event section of the Case Report Form. All clearly related signs and symptoms should be recorded.

All adverse events occurring during the study period must be recorded. The clinical course of each event should be followed until resolution, stabilization, or until it has been ultimately determined that the study treatment or participation is not the probable cause. Serious adverse events that are still ongoing at the end of the study period must be followed up, to determine the final outcome. Any serious adverse event that occurs after the study period and is considered to be at least possibly related to the study treatment or study participation will be recorded and reported immediately.

8.3 Reporting of Serious Adverse Events and Unanticipated Problems

When and adverse event has been identified, the Principal Investigator and/or Investigators will take appropriate action necessary to protect the study participant and then document the event in the adverse event section of the Case Report Form. The Principal Investigator and/or Investigators will evaluate the event and determine the necessary follow-up and reporting required.

8.3.1 Investigator reporting: notifying the Mayo Clinic IRB

The Principal Investigator and/or Investigators will report, as soon as possible, but no later than 5 working days after first learning of the problem/event, to the Mayo Clinic IRB any UPIRTSOs and Non-UPIRTSOs according to the Mayo Clinic IRB Policy and Procedures.

Documentation of adverse events will include the following information collected in the adverse event section of the case report form (and entered into the research database):

- •Subject's name
- •Medical record number
- Disease
- The date the adverse event occurred
- •Description of the adverse event
- •Relationship of the adverse event to the research
- •If the adverse event was expected
- The severity of the adverse event (defined by a severity scale)
- •If any intervention was necessary
- •Resolution (was the incident resolved spontaneously, or after discontinuing treatment)
- Date of resolution

The Principal Investigator and/or Investigators will review all adverse event reports to determine if specific reports need to be made to the IRB and FDA. The Principal Investigator and/or Investigators will sign and date the adverse event report when it is reviewed. For this protocol, only directly related SAEs/UPIRTSOs will be reported to the IRB.

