8.3.2 Investigator reporting: Notifying the FDA

This protocol is being conducted under an FDA investigational new drug application. The sponsor-investigator will report to the FDA all unexpected, serious suspected adverse reactions according to the required IND Safety Reporting timelines, formats and requirements. Unexpected fatal or life threatening suspected adverse reactions where there is evidence to suggest a causal relationship between the study drug/placebo and the adverse event, will be reported as a serious suspected adverse reaction. This will be reported to the FDA on FDA Form 3500A, no later than 7 calendar days after the sponsor-investigator's initial receipt of the information about the event.

Other unexpected serious suspected adverse reactions where there is evidence to suggest a causal relationship between the study drug/placebo and the adverse event, will be reported as a serious suspected adverse reaction. This will be reported to the FDA on FDA Form 3500A, no later than 15 calendar days after the sponsor-investigator's initial receipt of the information about the event.

Any clinically important increase in the rate of serious suspected adverse reactions over those listed in the protocol or product insert will be reported as a serious suspected adverse reaction. This will be reported to the FDA on FDA Form 3500A no later than 15 calendar days after the sponsor-investigator's initial receipt of the information about the event. The sponsor-investigator must also notify the FDA (and sponsors must notify all participating investigators) in an IND safety report of potential serious risks, from clinical trials or any other source, as soon as possible, but in no case later than 15 calendar days after the sponsor determines that the information qualifies for reporting under § 312.32(c)(1)(i)-(iv). Findings from other studies in human or animals that suggest a significant risk in humans exposed to the drug will be reported. This will be reported to the FDA on FDA Form 3500A, no later than 15 calendar days after the sponsor-investigators initial receipt of the information about the event.

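### The last sentence of Section 8.3.1 would keep UPIRTSOs that are possibly, but not directly, related from reaching the IRB

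*Combined protocol and SAP*

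**What the plan says.** Four places in the combined protocol and SAP bear on this.

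- **Section 8.1 (Definitions).** A UPIRTSO must be serious, unanticipated and related. An event counts as related "if it is possibly related to the research procedures".
- **Section 8.3.1, opening sentence.** The investigators report "to the Mayo Clinic IRB any UPIRTSOs and Non-UPIRTSOs according to the Mayo Clinic IRB Policy and Procedures", and must do so "no later than 5 working days after first learning of the problem/event".
- **Section 8.3.1, closing sentence.** "For this protocol, only directly related SAEs/UPIRTSOs will be reported to the IRB".
- **Section 8.2 (Recording of Adverse Events).** A serious adverse event (SAE) arising after the study period is to be recorded and reported at once if it is thought at least possibly related to treatment or participation. No recipient is named.

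Section 8.3.1 also lists "Relationship of the adverse event to the research" among the items to document, without giving categories for it. It leaves the decision to the investigators, who "will review all adverse event reports to determine if specific reports need to be made to the IRB and FDA".

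**The concern.** Section 8.3.1 gives the investigators two rules for the same decision. The opening rule takes in every UPIRTSO. The closing rule adds a relatedness filter that appears nowhere else and is not defined. If *directly* means more than *possibly*, the closing rule removes some of the events that the Section 8.1 definition was written to capture.

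What is at stake is participant protection, not the efficacy result. Section 8.6 places safety oversight with the investigators, and the documents name no safety committee for this trial. Reports to the IRB are therefore one of the few ways in which an individual event gets outside review. A serious, unforeseen event of uncertain cause is the kind for which that review is most useful.

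**Working it through.** No arithmetic applies, and the plan states no figure to reproduce. The check sets the texts side by side and follows a test event through them.

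**Step 1: thresholds for relatedness**

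| Place | Threshold | Use |
|---|---|---|
| 8.1 | possibly related to research procedures | defines a UPIRTSO |
| 8.2 | at least possibly related to treatment or participation | post-study SAEs, recipient not named |
| 8.3.1, opening | none beyond the UPIRTSO definition; IRB policy invoked | report to IRB |
| 8.3.1, closing | directly related, undefined | report to IRB |

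The closing sentence of 8.3.1 is the only one of these to use the stricter term.

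**Step 2: a test event.** Take an event that is serious, unanticipated, and judged possibly but not directly related to the research.

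- Under 8.1 it meets all three criteria, so it is a UPIRTSO.
- Under the opening sentence of 8.3.1 it goes to the IRB within 5 working days.
- Under the closing sentence, with *directly related* applied to both SAEs and UPIRTSOs, it is not reported.
- Under the closing sentence, with *directly related* applied to SAEs alone, it is reported because it is a UPIRTSO.

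The first reading of the closing sentence is the natural one, since the two terms are joined by a slash and share one modifier. On that reading the two sentences give opposite instructions for this event.

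**Step 3: does another section fill the gap?**

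- Section 8.2 requires all adverse events to be recorded, so the event stays on file. But its immediate-reporting rule covers SAEs after the study period and does not say who receives the report.
- Section 8.3.2 sends unexpected serious suspected reactions to the FDA "where there is evidence to suggest a causal relationship between the study drug/placebo and the adverse event". That is a test of drug causality and a different recipient. A UPIRTSO can instead arise from research procedures, and the list of serious problems in 8.1 extends to "breach of confidentiality and (7) other problems, events, or new information". FDA reporting is thus a partial backstop. The confidentiality item shows only that the two routes differ in scope: a breach of study data would ordinarily be directly related, and so reportable under the closing sentence as well.

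Neither section restores the IRB report for the test event.

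**Step 4: Non-UPIRTSOs.** The opening sentence sends these to the IRB as IRB policy requires. The closing sentence would send only those that are directly related SAEs. Whether the two differ depends on what the policy asks for, and the policy is not in the documents. This comparison cannot be completed.

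**The case against.** Several points can fairly be made for the plan.

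- **The closing sentence may be a deliberate, protocol-specific narrowing.** Its opening words allow this. But the text does not say that it overrides the first sentence, which still covers any UPIRTSO, and a deliberate narrowing would still need a definition of its key term.
- **The modifier may attach only to SAEs.** On that reading all UPIRTSOs are reported and the mismatch with 8.1 disappears. This is possible but is the less natural reading, and investigators should not have to choose between readings.
- **Section 8.1 defines and does not instruct.** This is correct. The mismatch with 8.1 lies in the relatedness threshold. The conflicting reporting instructions are both in 8.3.1.
- **The practical weight is small.** This also stands. The study is single-centre, enrols 10 patients, applies a topical cream for two weeks, and is described in Section 8.5 as low risk.

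A reader might go further and infer that the two sentences of 8.3.1 contradict each other however they are read, because the closing one shuts out Non-UPIRTSOs that the opening one names. The documents do not support that. The opening sentence is qualified by IRB policy. If that policy asks for no individual report of non-serious or unrelated events, the closing sentence takes nothing away for them. For the same reason, a count of the event classes on which the sentences disagree would depend on an unseen policy and would not measure anything.

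**Conclusion.** The point holds for one kind of event: a UPIRTSO judged possibly but not directly related. Followed as written and read naturally, the closing sentence of 8.3.1 would keep it from the IRB, although 8.1 defines it as a UPIRTSO and the opening sentence of 8.3.1 requires its report. The threshold is also out of line with the one in 8.2 for post-study SAEs.

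This rests on two assumptions: that *directly related* modifies both terms and means something stricter than *possibly related*, and that the IRB policy does not itself exempt possibly related UPIRTSOs. Nothing in the documents suggests such an exemption.

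The size cannot be put as a number, because no event rate is given. It should not be read as a prediction that reports will be missed; in a study this small there may be no such event. No conflict over Non-UPIRTSOs is claimed. This is a minor but real inconsistency in a safety rule, worth correcting because the correction is so small.

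**What to change.** Either of two changes to Section 8.3.1 is enough.

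1. Delete the closing sentence, so that the opening sentence and IRB policy govern.
2. Replace it with: *All UPIRTSOs as defined in 8.1 (including events possibly related to the research) will be reported to the IRB within 5 working days; Non-UPIRTSOs, including other SAEs, will be reported according to IRB policy.*

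Both remove the undefined term and bring IRB reporting of UPIRTSOs into line with 8.1. It is not necessary to impose the 5-day limit on every possibly related SAE. That would add a new rule for expected events without knowing whether IRB policy asks for it.

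The cost is one sentence of protocol text and possibly a few more IRB reports across 10 patients. No new data, visit or committee is needed, and endpoints, sample size and analysis stay as they are.
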